7.2 Definition of investigation sets

Full Analysis Set (FAS) will be composed of all randomised patients (according to ITT principle, i.e. analysed based on the initial treatment assignment), having used at least one dose of investigation medication and for whom at least one post-baseline performance evaluation will be available.

Per protocol set (PP) will be a subset of the FAS without major protocol deviation. The precise reasons for excluding patients from the PP set will be defined and documented before breaking the blind during the Blind Review Meeting.

Safety population will be composed of all patients exposed to the investigation drug, i.e. having used at least one administration of the investigation drug.

The **Eligible Eye** will be defined by following conditions:

- Oxford 0-15 score ≥ 4 and ≤ 9 AND;
- At least one of the following objective signs:
 - Schirmer test ≥ 3 mm/5 min and ≤ 9 mm/5 min,

Or

- Sum of 3 TBUT measurements ≤ 30 seconds.

For patients with both eligible eyes, the **Worst Eye** will be:

- Eye with the worst Oxford score;
- if same Oxford score in both eyes: eye with the worst Schirmer score;
- if same Oxford and Schirmer scores in both eyes: eye with the worst TBUT score;
- if same Oxford, Schirmer and TBUT scores in both eyes: right eye.

For patients with one eligible eye, the “worst eye” will be the eligible eye.

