3.3 Derived variables

Source data	Derivation rule	Label	Format
Possible impact of COVID-19 pandemic	If screening visit date (SVSTDT for VISITNUM=1 in SV table) <= 18MAR2020 Then IMPCOVID=0 If screening visit date > 18MAR2020 Then IMPCOVID=1	Possible impact of COVID-19 pandemic	1="Yes" 0="No"
Treated eye(s) at D35 and D84	If ECLOCLAT = Right eye, Left eye or Both eyes at least for one visit among Visit D35 and Visit D84, then SS=1 Else SS=0	Safety Set	1="Yes" 0="No"
Safety population, randomized status and post baseline performance evaluations	If SS=1 and DSRANDYN="Y" and at least one post basal value then FAS=1 Else FAS=0 Post basal value include: Oxford scores, Van Bijsterveld scores, DEQ-5 questionnaire, OSDI questionnaire, Schirmer test results, TBUT scores, BCVA, OSI and conjunctival hyperaemia at visit D8, D35 and D84	FAS population	1="Yes" 0="No"
FAS population and major deviation	If FAS=1 and MAJDEV=0 Then PP=1 Else PP=0 MAJDEV refer to major deviation. All major deviations will be determined during the BR meeting	PP Population	1="Yes" 0="No"
Informed consent signed and screen visit performed	If ICYN = "Y" And SVSTDT Ne "" (Where Visitnum=1) Then ENROLLED=1 If ICYN Ne "" Or S VSTDT = "" (Where Visitnum=1) Then ENROLLED=0	Enrolled Population	1="Yes" 0="No"
Oxford 0-15 score, Schirmer	To do for both eyes: If 4≤OXFGRTOT≤9 And (3≤ SCHIRM≤9 Or .< TBUTSUM≤30) Then ELIGEYE=1	Eligible eye	1="Yes" 0="No"

test and TBUT total score at D1	Else ELIGEYE=0		
Eligible eyes, Oxford scores, Schirmer scores, TBUT total scores at D1	
If only one eye is eligible, the eligible eye will be worst eye
 
If both eyes are eligible, then:
 
 - Eligible eye will be the eye with the worst Oxford score (maximum score of the eyes) - Else If same Oxford score in both eyes, eligible eye will be the eye with the worst Schirmer score (minimum score of the eyes) - Else If same Schirmer score in both eyes, eligible eye will be the eye with the worst TBUT score (minimum score of the eyes) - Else If same TBUT score in both eyes, eligible eye will be right eye. 
Else If same schirmer score in both eye, eligible eye will be the Right eye
	Worst eye	1="Right" 2="Left"
Worst eye	If WORST=1 Then CONTR=2 If WORST=2 Then CONTR=1	Contralateral eye	1="Right" 2="Left"

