Treatment period (in days) for D1-D35 and D35-D84	DURTT_TOT=SUM(DURTTi) i=D1-D35 and D35-D84 periods There is one line for D1-D35 period and one line for D35-D84 period. Two lines will be	Total treatment duration (in days)	Numeric (8.1)

	summed with SQL procedure in order to obtain total treatment period (in days)		
Age at Day 1	If . <AGE<65 Then AGEC=1 If 65≤AGE<85 Then AGEC=2 If AGE≥85 Then AGEC=3	Age (in classes)	1="< 65 years" 2="65; 85 years[" 3="≥ 85 years"
Date of Selection visit, Date of withdrawal,	STUDY_DUR_D= ENDDT – SVSTDAT (when visitnum=1)+1	Study duration (in days)	Numeric (8.1)
Mean Daily Dose Regimen at D1-D35 and D35-D84 periods	If ECREGIM="2" INSTILLATIONS/DAY" Then ECREGIMn=2 If ECREGIM="3"INSTILLATIONS/DAY" Then ECREGIMn=3 If ECREGIM="4"INSTILLATIONS/DAY" Then ECREGIMn=4 If ECREGIM ="5" INSTILLATIONS/DAY" Then ECREGIMn=5 If ECREGIM="MORE THAN 5" Then Do If exact number of dose are specified in ECREGIMS Then ECREGIMn=Input(ECREGIMS, 8.) If range of number of dose are specified, Then ECREGIMn=Round(mean of the range, 1) As ECREGIMS is a characters variable, mean will be calculated individually This derivation rule is valid for D1-D35 and D35-D84 periods	Mean Daily Dose Regimen (n)	Numeric (8.1)
Oxford total score at Day 1, Oxford Total score of the corresponding eye at Days 8, 35 and 84	BSOXFGRTOT=Oxford total score at D1 (OXFGRTOT) EVOL_OXFGRTOTi=(OXFGRTOBi – BSOXFGRTOT) i=Days 8, 35 and 84 (data are in line in the table)	Change from baseline in Oxford Grading Total score on Day i	Numeric (8.1)
Same derivation rule as above for change from baseline in Van Bijsterveld total score (VBGLOBSC and EVOL_VBGLOBSC)			
Items of DEQ-5 questionnaire at Selection visit, Day 35 and Day 84	If MULTQ51A="" Then DEQ501An=Input(DEQ501A, 8.) If DEQ501A="MISSING%" Or MULTQ51A Ne "" Then DEQ501An=. If MULTQ51B="" Then DEQ501Bn=Input(DEQ501B, 8.)	DEQ-5-Eye discomfort: How often? (n) DEQ-5-Eye discomfort:	Numeric (8.1)

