5.2 Generalities for statistical analyses

After the database lock and the randomisation code release, the statistical analysis will be performed by the statistician of Axonal-Biostatem, using SAS® software v9.4 (GUIDE, SAS Institute, North Carolina, USA), according to this SAP.

Disposition and baseline characteristics will be presented overall (globally) and by treatment groups. Performance and safety assessments and exposure/compliance will be presented by treatment groups.

Continuous variables will be summarised using descriptive statistics (number of non-missing data (n), number of missing observations, mean, standard deviation (SD), median, lower quartile (Q1), upper quartile (Q3), minimum and maximum).

Except minimum and maximum, descriptive statistics will be presented with one more decimal than the recorded value.

To compare treatment groups for ordinal qualitative variables, Cochran-Mantel-Haenszel (CMH) test will be used stratified by baseline values (if mentioned), with modified ridit scores and “row mean score differ” option. To compare treatment group when variable will be quantitative, Student T-test will be used, when data distribution will be assumed as normal (Shapiro-Wilk test for normality). If it is not the case, Mann-Whitney Wilcoxon test will be preferred instead.

Quantitative parameters will be also compared between groups using ANCOVA model. Furthermore, the mean change from baseline in total staining grade in the worst eye at Day 35 will be compared between the two treatments based on the MMRM analysis, which assumes:

- Data are Missing At Random (MAR)
- All the available data provide the information about non-observed data
- The treatment effect assume that the withdrawn patients mimic those who continued

Assumptions underlying the ANCOVA (respectively MMRM for the sensitivity analysis) will be checked:

- A histogram of residuals will be plotted to check the assumption of normality
- The underlying assumptions of normality of residuals will also be checked by using Shapiro-Wilk test
- Normal probability plot and QQ-plot will be performed to check the assumption of normality
- Residuals will be plotted against predicted values to check the assumption of heteroscedasticity
- For ANCOVA models, Levene's test will also be performed to check the homogeneity of variances

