6.1.2 Analysis Populations

Full Analysis Set (FAS) will be composed of all randomised patients (according to ITT principle, i.e. analysed based on the initial treatment assignment), having used at least one dose of investigation medication and for whom at least one post-baseline performance evaluation will be available.

Per protocol set (PP) will be a subset of the FAS without major protocol deviation. The precise reasons for excluding patients from the PP set will be defined and documented before breaking the blind during the BR meeting.

Safety population (SAF) will be composed of all patients exposed to the investigation Medical Device, i.e. having used at least one administration of the investigational Medical Device.

Note: Enrolled patients will be patients who have signed the informed consent and for whom the screening visit has been recorded in the e-CRF.

The **Eligible Eye** will be defined by following conditions:

- Oxford 0-15 score ≥ 4 and ≤ 9 AND;
- At least one of the following objective signs:
 - o Schirmer test ≥ 3 mm/5 min and ≤ 9 mm/5 min, **Or**
 - o Sum of 3 TBUT measurements ≤ 30 seconds.
 - o **And** without ophthalmological exclusion criterion

For patient with one eligible eye, this eye is considered as the “Worst eye” (study eye for primary analysis).

For patients with both eligible eyes or no eligible eye, the **Worst Eye** will be:

- Eye with the worst Oxford score;
- If same Oxford score in both eyes: eye with the worst Schirmer score;
- If same Oxford and Schirmer scores in both eyes: eye with the worst TBUT score;
- If same Oxford, Schirmer and TBUT scores in both eyes: right eye.

Note: worse Oxford score means highest value, whereas worse Schirmer score or worse TBUT score means lowest value.

The opposite to the worst eye is the **Contralateral Eye**.

Eligible eyes and Worst eye will be validated during the BR.

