6.7 Performance analyses

6.7.1 Primary Performance Endpoint

Primary performance endpoint will be analysed only in the worst eye.

Descriptive tables will be produced presenting selection, baseline (D1), Day 8, Day 35 and Day 84 Oxford Total score and change from baseline for Oxford Total score at Day 8, Day 35 and Day 84.

Oxford grade at each visit and change from baseline at Day 8, Day 35 and Day 84 will be also described for each panel: temporal bulbar conjunctiva, corneal area and nasal bulbar conjunctiva.

The hypothesis of non-inferiority of T2259 compared to Vismed® Multi will be tested by calculating the bilateral 95% CI of the difference between groups (T2259 – Vismed® Multi) of the change from baseline of Oxford Total Score on Day 35. A two-way analysis of covariance (ANCOVA) model will be constructed using main effects of investigation product and baseline score as covariate. Adjusted means by investigation product will be presented as well as an estimate of the difference between adjusted means.

A 95% two-sided confidence interval, based on the ANCOVA model (2), will be computed for the difference of T2259 minus Vismed® Multi. If the upper bound is no higher than 2 points for the PP population, it will be concluded that the null hypothesis can be rejected and that T2259 is non-inferior to Vismed® Multi.

The result will be presented as follow:

Population	T2259 (N=XX)	Vismed® Multi (N=XX)	Difference T2259 – Vismed Multi	SE of Difference T2259 – Vismed Multi	95% CI
Day 1 (baseline) mean (SD)	X1	Y1			
Day 35 mean (SD)	X2	Y2			
Adjusted mean change (SE) between Day 1 and Day 35	[X2- X1]*(SE)	[Y2-Y1]*(SE)	[X2-X1] -[Y2-Y1]	SE	[Min - Max**]

* These values were expected as negative, meaning an improvement of the Oxford score.

** The upper bound indicates the maximal difference of change in disfavour of T2259.

This analysis will be performed firstly on the Per Protocol population on the observed data.

Same analysis will be performed on FAS population with imputation of values in case of missing data with LOCF technique (Day 8 or value in case of withdrawal) and without imputation (observed cases) for confirmation.

The country and the investigation product-by-country interaction will be explored as a secondary analysis prior to presenting the final model (1).

Same analysis as principal analysis (ANCOVA model) will be performed adjusted on possible impact of COVID-19 pandemic (3).

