Another sensitivity analysis will be performed using MMRM model (4). This model will be constructed using main effects of investigation product and visit as factors and total Oxford baseline score as continuous covariate. Interactions between treatment and visit, treatment and baseline total Oxford score will also be included. REML method will be used and the covariance structure will be defined as unstructured: unstructured approach makes no assumption about the correlations among visits. If the analysis fails to converge, then spatial covariance, compound symmetry, or first order autoregressive model (A1) structure will be used. The best model fit will be determined by the AIC.

For the ANCOVA and MMRM analyses, the following MIXED procedure (SAS®) will be used.

Model	Method	SAS code
(1)	ANCOVA	<pre>PROC MIXED DATA=XX ORDER=DATA; WHERE PP = 1; /* OR FAS=1 */ CLASS TT COUNTRY; MODEL EVOL = TT BASELINE COUNTRY TT*COUNTRY / SOLUTION ALPHA=0.05; /* OTHER CHARACTERISTICS CAN BE ADDED HERE */ LSMEANS TT / DIFF=CONTROL CL OM; RUN;</pre>
(2)	ANCOVA	
Final model:
 <pre>PROC MIXED DATA=XX ORDER=DATA; WHERE PP = 1; /* OR FAS=1 */ CLASS TT; MODEL EVOL = TT BASELINE / SOLUTION ALPHA=0.05; /* OTHER CHARACTERISTICS CAN BE ADDED HERE */ LSMEANS TT / DIFF=CONTROL CL OM; RUN;</pre>
(3)	ANCOVA	<pre>PROC MIXED DATA=XX ORDER=DATA; WHERE PP = 1; /* OR FAS=1 */ CLASS TT COVID; MODEL EVOL = TT BASELINE COVID TT*COVID/ SOLUTION ALPHA=0.05; /* OTHER CHARACTERISTICS CAN BE ADDED HERE */ LSMEANS TT / DIFF=CONTROL CL OM; RUN;</pre>
(4)	MMRM	<pre>PROC MIXED DATA=XX METHOD=REML; WHERE PP=1; /* OR FAS=1 */ CLASS TT SUBJID VIS; MODEL EVOL = TT VIS BASELINE TT*VIS BASELINE*VIS / DDFM=SATTERTH SOLUTION ALPHA=0.05; REPEATED VISIT / TYPE=UN SUBJECT=SUBJID; LSMEANS TT*VIS / PDIFF CL;</pre>

```
ESTIMATE "D35 (VISIT 4) - DIFF T2259 - VISMED"  
TREATMENT 1 -1  
VISIT*TT 0 1 0 0 -1 0 / CL;  
ODS OUTPUT LSMEANS=MEANS DIFFS=DIF;  
RUN;
```

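### SAP 3.3 codes the Safety Set, and through it the FAS, from a Day 35 or Day 84 treated-eye record, which is narrower than the one-administration definition in SAP 6.1.2 and protocol 7.2

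*SAP*

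**What the plan says.** **The coded rule.** SAP 3.3 builds the Safety Set from the field ECLOCLAT, which must show a treated eye "at least for one visit among Visit D35 and Visit D84, then SS=1 Else SS=0". The next row makes a patient FAS only if SS=1, the patient was randomised and there is "at least one post basal value then FAS=1". The performance values that count there include those from Day 8. PP in turn requires FAS=1.

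**The definitions.** SAP 6.1.2 reads: "Safety population (SAF) will be composed of all patients exposed to the investigation Medical Device, i.e. having used at least one administration". Protocol 7.2 likewise takes "all patients exposed to the investigation drug, i.e. having used at least one administration of the investigation drug". Neither sets a visit condition. The FAS text in both documents adds one post-baseline performance evaluation.

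**Where exposure is recorded.** Protocol 6.8.4 has compliance checked at Day 35 and Day 84. For treatment duration SAP 3.3 notes: "There is one line for D1-D35 period and one line for D35-D84 period". The Day 8 visit is optional.

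**Where Day 8 data are used.** SAP 6.7.1 confirms the primary result in the FAS with the "LOCF technique (Day 8 or value in case of withdrawal"). Its MMRM contrast, "VISIT*TT 0 1 0 0 -1 0 / CL", carries three visit coefficients per arm, so Day 8 is in the model. SAP 5.2 states for that model: "All the available data provide the information about non-observed data".

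**The concern.** The text and the programming rule give different answers for an exposed patient who has no Day 35 or Day 84 exposure record. Followed literally, the rule resolves a missing record as no exposure.

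For a patient last seen at Day 8, the SAP also works against itself. It counts the Day 8 value as post-baseline and provides for carrying it forward, but the nesting of FAS in SS can remove that patient before either provision applies.

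Adverse events are at stake too. SAP 3.3 calls an event treatment-emergent from its onset relative to DAKDATD1, whatever the value of SS. An event can therefore be a TEAE in a patient coded SS=0. It would then fall outside Safety-population Tables 6.1 to 6.22 and Listings 7 to 12, and outside Listings 13 and 14, which hold only non-emergent events. Patients may stop early because of an adverse event (protocol 6.7.3), so losing such patients could understate event rates.

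**Working it through.** **1. The plan's own figures.** No figure in the plan depends on this rule. The SD (2.5) and margin (2) used below come from the sample-size section, which reproduces: 76 / 0.85 = 89.4, rounded up to 90. Power at 38 per group is 93.1% by the noncentral t, consistent with the stated minimum of 90%. Nothing here changes those figures.

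**2. Text against code.** All patients below are randomised and have confirmed use.

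| Patient path | Safety, text | Safety, code | FAS, text | FAS, code |
|---|---|---|---|---|
| Completes the study | in | in | in | in |
| Withdrawal visit on the Visit 5 form, treated eye recorded | in | in | in | in |
| Same, but the exposure record moves when the visit is re-labelled Day 8 | in | out | in | out |
| Last seen at Day 8, no later exposure record | in | out | in | out |
| No visit after Day 1, no later exposure record | in | out | out | out |

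Row 3 is conditional. SAP 4.3 and 6.2 allow a withdrawal visit to be re-labelled Day 8, but do not say whether ECLOCLAT moves with it. Rows 4 and 5 assume that no exposure line was entered without an attended visit, which cannot be checked without the e-CRF.

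**3. Outputs affected.** Rows 3 to 5 leave the safety summary tables. Rows 3 and 4 also leave the FAS-LOCF confirmation (Table 5.4c), the FAS MMRM (Table 5.6b) and the Day 8 FAS analyses (e.g. Table 5.7b). None of these patients has an observed Day 35 value, so none could enter the observed-data PP primary ANCOVA under either reading.

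**4. Scale for TEAE rates (illustration).** SAP 5.1 gives 101 randomised at 1:1, so take 50 per arm, x of them with a TEAE, and code out one patient.
- The patient had a TEAE: x/50 − (x−1)/49 = (50−x)/2450. This is 2.00 percentage points at x=1, 1.63 at x=10, 1.02 at x=25 and 0 at x=50.
- The patient had none: x/49 − x/50 = x/2450. This is 0.04 points at x=1, 0.41 at x=10, 1.02 at x=25 and 2.00 at x=49.
- For k patients in one arm, the maximum over all x is k/50: 2, 4 and 6 points for k = 1, 2, 3.

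**5. Scale for FAS-LOCF (illustration).** Suppose the coded-out patient lies 2 SD = 2 × 2.5 = 5 points from the mean of the others. The arm mean moves by 5/50 = 0.10 point, which is 0.10/2 = 5% of the margin. Three such patients, all in the same direction and arm, move it by 0.30 point (15%). For comparison, the 95% CI half-width at 50 per arm is t(98) × 2.5 × √(2/50) = 0.99.

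**The case against.** **The field is a proxy for use.** SAP 6.6 gives patients without any treated eye a mean daily dose of 0, so ECLOCLAT is meant to separate users from non-users. The definition requires use, and dispensing alone does not meet it. This stands for patients with no visit after Day 1: their use is normally unverified, and they are wrongly excluded only if it is confirmed. It does not rescue the rule for a confirmed user last seen at Day 8.

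**Few patients can be affected.** Protocol 6.7.3 asks for the final-visit examinations at early discontinuation, and dose-regimen compliance is asked on that form, so most early withdrawals should keep SS=1. This stands, and the count may be zero.

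**Blind review will catch it.** Protocol section 10 brings set exclusions to that meeting, and SAP 6.1.1 builds the analysis-set datafile from its decisions. Single cases could be corrected there, but neither passage says that the meeting replaces the 3.3 derivation.

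**LOCF and MMRM still use Day 8.** A patient with Day 8, a missed Day 35 and an exposure record at an attended Day 84 keeps SS=1 and contributes. The MMRM statement in SAP 5.2 is a missing-data assumption and does not define set membership. Both points are right. The conflict is confined to patients with no later exposure record.

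**The size is constructed.** No document gives the number affected or how far such patients lie from the mean. That is correct, and the figures show scale only.

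**Conclusion.** The SAP is internally inconsistent: the rule in 3.3 is narrower than the definition in 6.1.2, and it is wrong as written for a confirmed user whose last record is at Day 8. The consequence depends on e-CRF behaviour that the documents do not show. The per-patient shifts (up to 2.0 points in an arm's TEAE rate, about 0.10 point in the FAS-LOCF arm mean) are illustrations at 50 per arm and a 2-SD deviation. They are not estimates.

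Three stronger readings are not supported.
- *An undeclared change to the protocol.* A reader might infer this because SAP 4.3, which lists changes, is silent on it. But SAP 6.1.2 keeps the protocol's definition in substance, so no change of definition needed declaring. The fault is in how the SAP implements it.
- *Hidden patients or adverse events.* The adverse-event and exposure listings of SAP 5.2 name no population and show each patient's sets. SAP 6.2 reports reasons for exclusion from the safety population and lists all patients, and Tables 1.6a and 1.7a and Listing 1 cover randomised or screened patients. What is lost is the patient's place in the summary rates.
- *A threat to the primary conclusion.* The observed-data PP ANCOVA cannot change, because these patients have no Day 35 value.

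**What to change.** In SAP 3.3:
1. Set SS=1 for any randomised patient with recorded evidence of at least one IMD instillation at any time. Accept any IMD exposure record, including one from the withdrawal visit, and take it before visits are re-labelled.
2. Accept the Day 1 instillation date (DAKDATD1) as well, once it is confirmed that DAKDT records instillation. The check is needed because DAKDATLAST, derived from the same field, is labelled as a dispensation date.
3. Derive FAS from the corrected flag.
4. Settle every patient with unconfirmed use at blind review under the 6.1.2 definition, by the same criterion whether or not symptoms were reported. Do not let a positive Day 8 report of a sensation upon instillation admit a patient automatically. Section 3.3 creates zero lines for patients without symptoms, so only symptomatic patients would enter that way, and the safety denominator would depend on a safety outcome.

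The cost is one derivation rule and one check of a field definition, before database lock. The sources are fields that SAP 3.3 already uses. Appendix 1 already requires double programming of the populations, but that would reproduce the written rule and so would not catch this error.

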Discontinuations due to adverse events include drug related AE leading to premature IMP drug OR study withdrawal (i.e. drug related AE with action taken = drug withdrawn OR End of study with premature discontinuation due to this AE) will be listed.

Patient data listings of COVID-19 AEs (PT: COVID-19, Coronavirus infection) will also be produced.

Individual patient data listings of non-emergent AEs will be performed on the SAF population, separately for ocular and systemic AEs.

A excel file with relevant information will also be performed for the CSR narrative.

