8.2 Planned listings

Listings 3 and 4 will include PP and FAS populations (as variable) and listing 5 will include FAS population.

Part 6.2:

Listing 1: Non-selected patients, non-included patients and early withdrawals – All screened patients
Listing 2: Protocol deviations – FAS population

Part 6.3:

Listing 3: Other aetiology of Dry Eye – Safety population

Part 6.5:

Listing 4: Previous and concomitant treatments – Safety population

Part 6.6:

Listing 5: Daily dose regimen different from 2 to 4 instillations/day – Safety population

Part 6.7:

Listing 6: OSI score – FAS population

Part 6.8:

- Listing 7: Listing of individual data of overall systemic TEAEs – Safety population
- Listing 8: Listing of individual data of overall ocular TEAEs – Safety population
- Listing 9: Listing of individual data of overall systemic SAEs – Safety population
- Listing 10: Listing of individual data of overall ocular SAEs – Safety population
- Listing 11: Listing of individual data of overall systemic SADEs – Safety population
- Listing 12: Listing of individual data of overall ocular SADEs – Safety population
- Listing 13: Listing of individual data of non-emergent systemic AEs – Enrolled population
- Listing 14: Listing of individual data of non-emergent ocular AEs – Enrolled population
- Listing 15: Listing of COVID-19 AEs – Enrolled population

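### SAP 3.3 as printed gives no consenting patient ENROLLED=1, and SAP 6.8.2 and 8.2 name different populations for the non-emergent adverse event listings

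*SAP*

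**What the plan says.** SAP 3.3 derives ENROLLED with two consecutive statements. The first assigns 1 when the consent variable ICYN equals 'Y' and the date of Visit 1 is present. The second has no Else before it. It assigns 0 when ICYN is not equal to blank, or when the date is blank, and it ends "Where Visitnum=1) Then ENROLLED=0".

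SAP 6.1.2 gives the intended meaning in prose: "Enrolled patients will be patients who have signed the informed consent and for whom the screening visit has been recorded in the e-CRF".

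SAP 8.2 uses this population for three of the nine adverse event listings. Two of them, numbers 13 and 14, hold the non-emergent events, systemic and ocular in turn. The title of the first is "Listing of individual data of non-emergent systemic AEs – Enrolled population", and that of the second differs only in the type of event. The remaining one is "Listing 15: Listing of COVID-19 AEs", which carries the same population label.

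Listings 7 to 12 are all on the Safety population.

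SAP 6.8.2 says something different about the non-emergent events: "Individual patient data listings of non-emergent AEs will be performed on the SAF population". It also promises a COVID-19 listing, without naming a population for it.

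Protocol 14.1.5 and 14.2 start adverse event recording at signature of consent. Protocol 6.4.2 has the investigator ask about run-in events at the randomisation visit.

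**The concern.** There are two separate faults. The flag rule does not produce the population that the SAP defines in words. In addition, two SAP sections give different populations for the same listings and cannot both be followed.

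What is at stake is the display of events before the first device instillation, above all in patients who consented, entered the run-in and were never treated. Listings 7 to 12 cannot show those patients, because the Safety population requires device exposure. Listings 13 to 15 are the only numbered adverse event listings that could, and they do so only if the Enrolled population is both correctly derived and actually used.

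**Working it through.** The plan gives no figure to reproduce, so the check is a trace of the logic followed by a comparison of the sections.

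**Step 1: trace the flag.** The inputs are ICYN (Y, N or blank) and the Visit 1 date (present or blank), both from SAP 3.3. Three versions were run:
- as printed: two consecutive statements, the last true one wins
- with an Else placed before the second statement
- with the second condition changed to `ICYN Ne 'Y' Or SVSTDT = ''`

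| ICYN | Visit 1 date | As printed | With Else before second If | Corrected condition |
|---|---|---|---|---|
| Y | present | 0 | 1 | 1 |
| Y | blank | 0 | 0 | 0 |
| N | present | 0 | 0 | 0 |
| N | blank | 0 | 0 | 0 |
| blank | present | unassigned | unassigned | 0 |
| blank | blank | 0 | 0 | 0 |

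As printed, none of the six combinations ends at 1. In the first row the first statement gives 1; the second is then also true, because 'Y' is not blank, and replaces it with 0. A filter on ENROLLED=1 therefore selects nobody. The corrected condition gives 1 only for consent with a visit date, which is the definition in 6.1.2. A plain Else, with no condition after it, gives the same result.

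**Step 2: follow the flag into the listings.**

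| Listing | Population in 8.2 | Population in 6.8.2 | Result if 8.2 is followed with the printed flag | Result if 6.8.2 is followed |
|---|---|---|---|---|
| 13, non-emergent systemic | Enrolled | Safety | empty | treated patients only |
| 14, non-emergent ocular | Enrolled | Safety | empty | treated patients only |
| 15, COVID-19 | Enrolled | none named for this listing | empty | no alternative named |

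**Step 3: a run-in event in a patient never treated.** Listings 7 to 12 exclude the patient as not exposed. Listings 13 to 15 select nobody if 8.2 is followed with the printed flag. Listings 13 and 14 exclude the patient as not exposed if 6.8.2 is followed. The event is therefore in none of Listings 7 to 15 on either route.

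**Step 4: look for wider effects.** In SAP 3.3 the Safety flag is built from the treated-eye record at Day 35 or Day 84. FAS is built from the Safety flag, randomisation and a post-baseline value. PP is built from FAS and major deviations. ENROLLED enters none of them.

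**The case against.** **The table is a specification, not runnable code, and the intent is plain.** The source column of the same row and SAP 6.1.2 both say consent plus screening visit, so a programmer would know what is meant. That is fair, and it makes the slip easy to correct. But the Safety, FAS, PP and eligible-eye rules in the same table write Else explicitly and this one does not. Even with an Else before the second statement, a blank consent field with a visit date is left unassigned.

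**Double programming would catch it.** SAP Appendix 1 puts populations and derived data at the critical level, and a flag of 0 for all 101 randomised patients would be conspicuous. That makes an empty final listing less likely. It does not correct the rule, and two programmers who follow the text literally would agree with each other.

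**A character may have been lost between the quotation marks when the PDF was read.** This cannot be excluded. It would remove the flag error but not the conflict between 6.8.2 and 8.2.

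**Stronger readings.** A reader might infer that all three listings are certain to be empty. The documents do not support that: under 6.8.2, Listings 13 and 14 run on the Safety population, whose flag is untouched. A reader might also infer that the events are reported nowhere. That goes too far as well:
- SAP 5.2 promises general data listings of all recorded assessments, adverse events included.
- Listing 1 covers all screened patients. SAP 6.2 has adverse event among the coded reasons for non-inclusion, so an event that prevented inclusion could appear there as a reason.
- SAP 6.8.2 mentions further listings of deaths and other serious events for narratives, without naming a population for them.
- Treatment-emergent COVID-19 events in treated patients are already in Listings 7 and 8, and serious ones in 9 and 10. An empty Listing 15 would lose a separate display, not those events.

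**Conclusion.** The point holds as a minor specification and consistency error. As printed and run in order, the rule leaves no consenting patient in the Enrolled population. Listing 15 would then be empty, and Listings 13 and 14 would be empty if 8.2 governs. If 6.8.2 governs, Listings 13 and 14 omit only patients who never received the device. On both routes, run-in events in those patients are missing from the planned adverse event Listings 7 to 15.

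This rests on two assumptions: that the statements are executed in sequence without an Else, and that the second condition in the source document really compares ICYN with blank. The conflict between 6.8.2 and 8.2 needs neither. The documents do not say how many patients had a run-in event without being treated, so the number of events affected is unknown.

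No performance result and no treatment-emergent event table changes.

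**What to change.** 1. In SAP 3.3, change the second condition to `ICYN Ne 'Y' Or SVSTDT = ''`, or replace it with a plain Else.
2. In SAP 6.8.2, name the Enrolled population for the non-emergent and the COVID-19 adverse event listings. This matches 8.2 and the collection period in the protocol.
3. While editing, state that an event in a patient with no first instillation date counts as non-emergent. SAP 3.3 classifies events by comparing onset with that date and does not cover its absence. If a missing date is treated as the lowest value, as SAS does, a dated event in a never-treated patient would be coded treatment-emergent and could still miss Listings 13 and 14.

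The cost is a few words of SAP text and one line of code. No new data are needed.
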